6.1.3.12.1 Medical Outcomes Study 36-Item Short-Form Health Survey (SF-36)

The Medical Outcomes Study 36-Item Short-Form Health Survey (SF-36) is a multi-purpose, short-form health survey with 36 questions (see [Appendix 1](#)). It yields an 8-scale profile of functional health and well-being scores as well as psychometrically-based physical and mental health summary measures. It is a generic measure, as opposed to one that targets a specific age, disease, or treatment group. Accordingly, the SF-36 has proven useful in surveys of general and specific populations, comparing the relative burden of diseases, and in differentiating the health benefits produced by a wide range of different treatments.

The SF-36 contains 36 items that measure eight dimensions or scales: (1) physical functioning (PF); (2) role limitations due to physical health problems (RP); (3) bodily pain (BP); (4) social functioning (SF); (5) general health perceptions (GH); (6) role limitations due to emotional problems (RE); (7) vitality, energy or fatigue (VT); and (8) mental health (MH) (see [Appendix 1](#)). In addition, two summary measures, defined as the Physical Component Score (SF-36 PCS) and Mental Component Score (SF-36 MCS) will be provided.

Scoring of each dimension and the summary measure will be performed by QualityMetric using QualityMetric Health Outcomes(tm) Scoring Software 4.5.

Change from baseline to the average value in weeks 12-28 will be calculated for the Physical Component Scores of SF-36 (SF-36 PCS), following the same rules as defined in Section [6.1.2.4](#)

For missing SF-36 PCS values, refer to Section [7.11.1](#) imputation rules. Baseline always refers to the assessment at day 1 to be performed prior to first study drug administration.

The number and percent of subjects with a change from baseline of $<3 / \geq 3$ points and of $<5 / \geq 5$ points will be calculated for each visit for the following: Vitality Score (SF-36 VT), Physical Functioning score (SF-36 PF) and Physical Component score (SF-36 PCS).

In addition, the eight dimensions and the two summary measures and their associated change from baseline will be reported by visit.

The normalized values will be used for analysis.

6.1.3.12.2 Functional Assessment of Cancer Therapy –Anemia (FACT-An)

The Functional Assessment of Cancer Therapy – General (FACT-G; version 4) contains 27 items that cover four dimensions of well-being: physical (PWB) – 7 items, functional (FWB) – 7 items, social/family (SWB) – 7 items, and emotional (EWB) – 6 items.

The ‘additional concerns’ section contains 20 items: 13 fatigue specific items plus 7 additional items related to anemia were developed for use in conjunction with the FACT-G (Cella 1997). The 13 fatigue items plus the seven additional items related to anemia comprise the Anemia Subscale (AnS). Administration of the FACT-G plus the Anemia Subscale (AnS) is referred to as the FACT-An. The FACT-An has a recall period of the ‘past seven days’. Respondents are asked to provide responses, (i.e., ‘Not at all’, ‘A little bit’, ‘Somewhat’, ‘Quite a bit’ and ‘Very much’), to a list of statements which are either positively or negatively phrased. A final higher score indicates better QoL (see [Appendix 2](#)).

Each individual item is scored from 0 (Not at all) to 4 (Very much), and then the total score is obtained by summation of the resulted scores.

If there are missing items, subscale scores can be standardized. This is done by multiplying the sum of the subscale by the number of items in the subscale, then dividing by the number of items actually answered. This can be done on the scoring guide or by using the formula below:

Prorated subscale score = [Sum of item scores] x [N of items in subscale] / [N of items answered]

When there are missing data, standardizing by subscale in this way is acceptable (Webster 2003) as long as more than 50% of the items were answered (e.g., a minimum of 4 of 7 items, 4 of 6 items, etc). The total score is then calculated as the sum of the un-weighted subscale scores. The FACT scale is considered to be an acceptable indicator of a subject’s quality of life as long as overall item response rate is greater than 80% (e.g., at least 22 of 27 FACT-G items completed). This is not to be confused with individual subscale item response rate, which allows a subscale score to be prorated for missing items if greater than 50% of items are answered. In addition, a total score should only be calculated if ALL of the component subscales have available scores.

The FACT-An instrument will be scored according to [Appendix 10.2](#). The following 8 scores will be calculated:

- PWB subscale score
- SWB subscale score

- EWB subscale score
- FWB subscale score
- AnS subscale score
- FACT-An TOI score
- FACT-G total score
- FACT-An total score
- Fatigue subscale score

Change from baseline to the average value in weeks 12-28 will be reported for the two scores (Anemia subscale ‘Additional concerns’ of FACT-An score and Total FACT-AN score). In addition, the score and change from baseline will be reported for each visit for all six scores.

Change from baseline to the average value in weeks 12-28 will be calculated for the FACT-An subscore following the same rules as defined in Section 6.1.2.4

No imputation will be performed in case of a missing value.

Baseline always refers to the assessment at day 1 to be performed prior to first study drug administration.

6.1.3.12.3 EQ-5D 5L

The EQ-5D 5L is an international standardized non-disease specific (i.e. generic) instrument for describing and valuing health status, and a multi-dimensional measure of health-related QoL (see Appendix 10.3).

It includes two main components: (1) a VAS scale rating perception of overall health and (2) 5 qualitative domains: Mobility, Self-Care, Usual Activities, Pain/Discomfort, and Anxiety/Depression. For more details and description of the questionnaire, refer to Appendix 10.3

Change from baseline to the average value in weeks 12-28 will be calculated for the EQ 5D 5L VAS, following the same rules as defined in Section 6.1.2.4

Frequency distributions will be described for each visit for:

- EQ-5D 5L Mobility Score
- EQ-5D 5L Self-Care Score
- EQ-5D 5L Usual Activities Score
- EQ-5D 5L Pain/Discomfort Score
- EQ-5D 5L Anxiety/Depression Score

The evaluation period for the VAS score is defined as the average of available EQ-5D 5L VAS scores of weeks 12-28 (visit at W12 and W28).

No imputation will be performed in case of a missing item. Baseline always refers to the assessment at day 1 to be performed prior to first study drug administration.

6.1.3.13 Patients' Global Impression of Change (PGIC)

The Patients' Global Impression of Change (PGIC) is a subject-rated instrument that measures change in subjects' overall status since the start of the study on a 7-point qualitative scale ranging from 1 (very much improved) to 7 (very much worse) (see Appendix 10.4).

Data will be reported qualitatively by assessment as follows:

- Reported subject status,
- Combined Categories as binary:
 - Very Much Improved + Much Improved (yes/no)
 - Very Much Improved + Much Improved + Minimally Improved (yes/no)

No imputations will be performed in case of a missing item, except that the score at the last post-baseline assessment will be derived too.

6.1.3.14 Changes from BL to each study visit (when measured) in Serum hepcidin, Serum ferritin, TSAT and HbA1c level.

Changes from baseline to each study visit (see analysis windows in Table 32) will be calculated for these parameters:

- Serum hepcidin,
- Serum ferritin,
- TSAT,
- Serum Iron,
- Total Iron Binding Capacity (TIBC).
- HbA1c level (Subjects with and without diabetes in history, and overall),

For all variables listed above, baseline assessment is the assessment from Day 1 visit. If this value is missing, then the screening period value, if collected for that parameter, will be used.

6.1.4 Other exploratory variables: hs-CRP (High Sensitivity C-Reactive Protein) and Post-dialysis BP

The variable hs-CRP will be collected from the central laboratory on the following visits: Day 1, weeks 4, 12, 20, 36, 52, EOT and EOS. Absolute values and changes from baseline to each study visit will be calculated. Baseline assessment is the assessment from Day 1 visit. If Day 1 assessment is missing, change from baseline will not be reported. Analysis windows are defined in Table 32

Post-dialysis BP will be used to perform additional exploratory analyses for BP-related endpoints: 1) MAP and 2) Time to first occurrence of increase in blood pressure.

6.2 Safety Variables

Safety will be assessed by evaluation of the following variables:

- Treatment-emergent adverse events (TEAEs; frequency, severity, seriousness, and relationship to study drug), and pre-specified adjudicated cardiovascular and cerebrovascular events (will be reported separately),

- Vital signs (systolic and diastolic blood pressure, pulse, respiratory rate and weight),
- Clinical laboratory variables (hematology, biochemistry including liver enzymes and total Bilirubin),
- Physical examination,
- 12-lead electrocardiogram (ECG),
- Vascular Access Thrombosis.

The **Safety Emergent Period** will be defined as the evaluation period from the Analysis date of first drug intake up to 28 days after the Analysis Date of Last Dose taking into account the dosing frequency. Refer to Section [7.11.5](#) for more details on the derivation of the date of End of the Safety Emergent Period. This period will also be used to identify the minimum or maximum values collected on-treatment, defined as values collected from Day 2 up to the end of the Safety Emergent Period.

6.2.1 Adverse Events

6.2.1.1 Treatment emergent adverse event (TEAE)

TEAE is defined as an adverse event observed after starting administration of the test drug/comparative drug. If the adverse event occurs on Day 1 and the onset check box is marked “Onset after first dose of study drug” or the onset check box is left blank, then the adverse event will be considered treatment emergent. If the adverse event occurs on Day 1 and the onset check box is marked “Onset before first dose of study drug”, then the adverse event will not be considered treatment emergent. If a subject experiences an event both during the pre-investigational period and during the investigational period, the event will be considered as TEAE only if it has worsened in severity (i.e., it is reported with a new start date). All adverse events collected during the Safety Emergent Period will be counted as TEAE.

A drug-related TEAE is defined as any TEAE with at least possible relationship to study treatment as assessed by the investigator or with missing assessment of the causal relationship.

Severity of AEs will be graded according to National Cancer Institute - Common Terminology Criteria for Adverse Events (NCI-CTCAE) Version 4.0.

For AE onset date imputation rules, refer to Section [7.11.2](#)

All adverse events will be coded using the Medical Dictionary for Regulatory Activities (MedDRA) version 20.0.

6.2.1.2 Standardized MedDRA Queries

No standardized MedDRA Queries (SMQs) will be performed.

6.2.1.3 Time to occurrence of a TEAE (by type of AE group)

TEAEs are classified into a number of groups depending on the following factors:

- Serious TEAEs
- Death during the Safety Emergent Period

- All deaths during study period and post study safety follow up period
- Related Serious TEAEs
- TEAEs Leading to permanent Discontinuation of study drug
- TEAEs NCI CTC(AE) Grade 3 or Higher
- MedDRA System Organ Class (SOC)

The time to occurrence for a subject with a TEAE for a given type (e.g., serious AE leading to discontinuation) will be calculated (in years) as:

$$\frac{(\text{First TEAE date of the given type during the Safety Emergent Period} - \text{Analysis date of first dose intake} + 1)}{365.25}$$

With 'Analysis date of first dose' defined in Section 6.5.4 All adverse events collected during the Safety Emergent Period will be counted as TEAE, irrespective of use of rescue therapy.

Subjects who have not experienced a TEAE for that given type will be censored; the subject will be censored and the time to censoring for these subjects will be calculated (in years) as:

$$\frac{(\text{Date of End of Safety Emergent Period} - \text{Analysis date of first dose intake} + 1)}{365.25}$$

With Date of End of Safety Emergent Period defined in Section 7.11.5

For any deaths during the 24-month period (including those occurring during the Post-Study Follow Up Period), time to occurrence for a subject who died during study / post study follow up) will be calculated (in years) as:

$$\frac{[\text{End date for corresponding Fatal AE} - \text{Analysis date of first dose intake} + 1]}{365.25}$$

With 'End date for corresponding Fatal AE' which cover both study and post-study FU occurring up to Day 760 (i.e., month 24 + one month follow up + 3 days window as per protocol).

Subjects who have not died; the subject will be censored and the time to censoring for these subjects will be calculated (in years) as:

$$\frac{(\text{Minimum between [Day 760 and Max (Date of last known date when subject alive (End of Post-study FU), Date of last contact (Post study FU visit/call), Date of last Study evaluation (EOS form)]} - \text{Analysis date of first dose intake} + 1)}{365.25}$$

6.2.1.4 Definition of incidence rate

The incidence rate (per 100 subject years at risk) will be calculated as follows:

$$\frac{\text{Number of subjects with event}}{\text{Total cumulative time at risk (years)}} \times 100$$

Where Total cumulative time at risk is the sum of individual time at risk defined as either time to occurrence of the event or time to censoring for subjects with no event.

Time to occurrence of the event and time to censoring are defined in Section 6.2.1.3

6.2.1.5 Definition of event rate

The event rate (number of events per 100 subject years) will be calculated as follows:

$$\frac{\text{Number of treatment - emergent events}}{\text{Total patient years (years)}} \times 100$$

Where Total patient years is the sum of individual time during the safety emerging period expressed in years.

6.2.1.6 Adverse events up to 7 days after last dose

Additional analyses restricted to any treatment-emergent adverse event starting up to Analysis Date of Last Dose (adjusted for dosing frequency) + 7 days will be conducted.

Time to occurrence of event will be calculated (in years) as:

(First event date of the given type occurring from Day 1 (post dose) up to Analysis date of Last Dose + X + 7 days) – Analysis date of first dose intake + 1) / 365.25, where X days is defined depending on the dosing frequency.

With ‘Analysis date of first dose intake’ Analysis Date of Last Dose defined in Section [6.5.4](#) and [7.11.5](#) Subjects who have not experienced an AE for that given type will be censored and the time to censoring for these subjects will be calculated (in years) as:

Minimum [Analysis Date of Last Dose + X + 7 days, *Max* (EOS, Date of Death)] – Analysis date of first dose intake + 1) / 365.25.

6.2.2 Vital Signs

The following endpoints will be assessed, pre and post dialysis:

- Systolic blood pressure (SBP)
- Diastolic blood pressure (DBP)
- Pulse

In addition, the following assessments will be done:

- Respiratory rate
- Weight

Single measurements for blood pressure (BP) will be taken at three visits during the screening period. Measurements will be taken in triplicate with 2-minute intervals for all other visits. An average will be calculated from the three readings, the average in the eCRF system will not be used. If less than three readings are available, the non-missing readings will be used in the calculation of the average.

The position and date for the assessment will also be recorded. Change from baseline will be calculated as the measurement taken at the specific visit minus the measurement at baseline visit.

For all vital parameters, the minimum and the maximum post-baseline value during the Safety Emergent Period will be defined. For this calculation, only values from day 2 up to the date of End of the Safety Emergent Period (see Section 7.11.5) will be used.

Baseline assessment is the assessment from day 1 visit. If day 1 assessment is missing, screening period assessment will be used in the analysis. For missing visits, the last observation will be carried forward.

For vital signs, if there are pre-dialysis and post-dialysis assessments, the pre-dialysis assessment will be used for classification of the analysis visit (see Section 7.11.4) and the definition of potentially clinical vital signs criteria will use pre-dialysis and post-dialysis assessments separately.

Vital signs values are potentially clinically significant (PCS) if they meet both the observed value criteria and the change from baseline criteria listed in Table 7 (10 combined criteria).

Table 7 Potentially Clinically Significant (PCS) Vital signs Criteria

Vital Sign Parameter	Flag	Criteria	
		Observed Values	Change from Baseline
Respiratory Rate (breaths per min)	High	≥ 20	Increase of ≥ 5
	Low	≤ 10	Decrease of ≥ 5
Systolic Blood Pressure (mmHg)	High	≥ 170	Increase of ≥ 20
	Low	≤ 90	Decrease of ≥ 20
Diastolic Blood Pressure (mmHg)	High	≥ 110	Increase of ≥ 15
	Low	≤ 45	Decrease of ≥ 15
Pulse (beats per min)	High	≥ 120	Increase of ≥ 20
	Low	≤ 50	Decrease of ≥ 20
Weight (kg)	High	-	Increase of ≥ 10%
	Low	-	Decrease of ≥ 10%

Potentially Clinically Significant Vital Signs Criteria will be calculated at each study visit and on-treatment (at any moment during the Safety Emergent Period) using the worst value among all available measurements.

Time to occurrence of PCS Vital signs:

For each potentially clinically significant vital signs criterion (i.e 10 combined criteria), the time to occurrence of a PCS at any moment during the Safety Emergent Period (see Section 6.2) will be calculated (in years) as:

$$(\text{First occurrence date} - \text{Analysis date of first dose intake} + 1) / 365.25$$

With ‘First occurrence date’ defined as the first date when both criteria (i.e., on observed and change from baseline) are met and Analysis date of first dose intake is defined in Section 6.5.4

Subjects without abnormality will be censored and time to censoring for these subjects will be calculated (in years) as:

(Date of last vital signs assessment where the parameter analyzed is non-missing during the Safety Emergent Period – Analysis date of first dose intake +1) / 365.25

6.2.3 Clinical laboratory variables

6.2.3.1 Potentially Clinically Significant (PCS) Laboratory Criteria

Laboratory test values are potentially clinically significant (PCS) if they meet either the low or high PCS criteria listed in Table 8 below.

Table 8 Potentially Clinically Significant (PCS) Laboratory Criteria

Potentially Clinically Significant Laboratory Criteria			
Laboratory Parameter	Unit	Low PCS Criteria	High PCS Criteria
Alanine Aminotransferase (ALT)	U/L	no lower limit	> 3X ULN > 5X ULN [#] > 8X ULN [#] > 10X ULN [#] > 20X ULN [#]
Aspartate Aminotransferase (AST)	U/L	no lower limit	> 3X ULN > 5X ULN [#] > 8X ULN [#] > 10X ULN [#] > 20X ULN [#]
Alkaline Phosphatase (ALP)	U/L	no lower limit	> 1.5 X ULN [#] > 3 X ULN [#]
ALT or AST > 8× ULN	U/L for ALT or AST	no lower limit	ALT or AST > 8X ULN
Total Bilirubin	µmol/L	no lower limit	> 1.5 X ULN > 2 X ULN [#]
Moderate Liver Abnormality*	U/L for ALT and AST, µmol/L for Total Bilirubin	no lower limit	ALT and/or AST > 3X ULN or Total Bilirubin > 2X ULN
Severe Liver Abnormality*	U/L for ALT and AST, µmol/L for Total Bilirubin	no lower limit	ALT and/or AST > 3X ULN and Total Bilirubin > 2X ULN
Gamma Glutamine Transaminase (GGT)	U/L	no lower limit	> 3X ULN
Calcium	mmol/L	< 0.8 X LLN	>1.2 X ULN
Creatinine	µmol/L		>1.5 X Baseline ^s
Potassium	mmol/L	< 0.75 X LLN	>1.2 X ULN
Sodium	mmol/L	< 0.9 X LNL	>1.1 X ULN
Total Protein	g/L	< 0.9 X LNL	>1.1 X ULN
Blood Urea Nitrogen (BUN)	mmol/L		>1.5 X Baseline ^s
Neutrophils	10 ⁶ /L	≤1000	
Platelet Count	10 ⁹ /L	≤100	≥700
White Blood Cell Count	10 ⁹ /L	≤2.5	≥15
Lipase	U/L	no lower limit	> 3X ULN or > 2 X Baseline ^s

LLN: Lower limit of normal, value provided by the laboratory
ULN: Upper limit of normal, value provided by the laboratory

Footnotes appear on next page

* a subject's ALT and Total Bilirubin laboratory draw date or AST and Total Bilirubin laboratory draw date must occur on the same blood sample in order to be counted.

Additional criteria required for summary of Liver Function Tests only (see Section 7.5.2.1).

§ Criteria of > nX baseline only applicable for post-baseline assessments.

Potentially Clinically Significant Laboratory Criteria will be calculated at each study visit and on-treatment (see Section 6.2) using the worst value among all available measurements, except for Moderate and Severe Liver Abnormalities which will be calculated on-treatment only.

Time to occurrence of an abnormality (for selected criteria)

Time to occurrence of an abnormality, will be derived only for the following PCS criteria:

- Alanine Aminotransferase (ALT) > 3X ULN
- Aspartate Aminotransferase (AST) > 3X ULN
- Total Bilirubin > 1.5 X ULN

For each above potentially clinically significant laboratory criteria, the time to occurrence of an abnormality for a subject with an abnormality at any moment during the Safety Emergent Period (see Section 6.2) will be calculated (in years) as defined in Section 6.2.2

Time to censoring will be defined (in years) as:

(Date of last laboratory assessment where parameter analyzed is non-missing during the Safety Emergent Period – Analysis date of first dose intake +1) / 365.25

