### Definition of Liver Abnormalities

Confirmed abnormalities will be characterized as moderate and severe where ULN:

Moderate	ALT or AST $> 3 \times \text{ULN}$	or	Total Bilirubin $> 2 \times \text{ULN}$
Severe*	$> 3 \times \text{ULN}$	and	$> 2 \times \text{ULN}$

In addition, the subject should be considered to have severe hepatic abnormalities for any of the following:

- ALT or AST  $> 8 \times \text{ULN}$
- ALT or AST  $> 5 \times \text{ULN}$  for more than 2 weeks
- ALT or AST  $> 3 \times \text{ULN}$  and International Normalized Ratio (INR)  $> 1.5$  (If INR testing is applicable/evaluated).
- ALT or AST  $> 3 \times \text{ULN}$  with the appearance of fatigue, nausea, vomiting, right upper quadrant pain or tenderness, fever, rash and/or eosinophilia ( $> 5\%$ ).

The investigator may determine that abnormal liver function results, other than as described above, may qualify as moderate or severe abnormalities and require additional monitoring and follow-up.

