7.5.2.1 Liver function tests

Descriptive summary of PCS values in Liver Enzymes and Total Bilirubin will be provided as per Astellas standard TLB_005.

In addition, a matrix scatter plot of Liver Enzymes and Bilirubin will be plotted showing the maximum ALT, AST, ALP and total bilirubin during the Safety Emergent Period crossed against each other. Different dots will be used for roxadustat and ESA.

Individual displays of Liver Enzymes and Bilirubin parameters, listed in Section [6.2.3.1](#) will be reported for all subjects with either ALT or AST > 3 x ULN or total bilirubin > 2 x ULN during the Safety Emergent Period.

For subjects who require further liver function investigations, additional information will be collected and listed.

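### SAP Table 8's Severe Liver Abnormality row holds one of the protocol's five severe criteria, so its by-arm count is not the protocol's severe category

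*SAP*

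**What the plan says.** SAP Table 8 has two composite liver rows. Moderate Liver Abnormality is "ALT and/or AST > 3X ULN or Total Bilirubin > 2X ULN"; Severe Liver Abnormality is "ALT and/or AST > 3X ULN and Total Bilirubin > 2X ULN". A footnote to both rows says that the transaminase and bilirubin results "must occur on the same blood sample in order to be counted". Other criteria are evaluated at each visit as well as on treatment, "except for Moderate and Severe Liver Abnormalities which will be calculated on-treatment only". A separate composite row covers "ALT or AST > 8X ULN". Single-enzyme thresholds above 5, 8, 10 and 20 times ULN are marked for the liver-test summary only. SAP Section 7.5.2 then reports, by treatment arm, the percentage of subjects meeting each criterion who did not meet it at baseline.

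Protocol Appendix 12.2 (Definition of Liver Abnormalities) has the same base pair for confirmed abnormalities: either elevation is moderate, both together are severe. It then extends severe: "In addition, the subject should be considered to have severe hepatic abnormalities for any of the following". Four items follow:

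- ALT or AST above 8 times ULN;
- ALT or AST above 5 times ULN lasting beyond 2 weeks;
- ALT or AST above 3 times ULN with INR above 1.5, where INR was tested;
- ALT or AST above 3 times ULN with listed symptoms, rash or eosinophilia.

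**The concern.** The same words name two different categories. In the protocol, severe has operational force. Section 5.4.2.1 requires contact with the medical monitor within 24 hours for a confirmed severe abnormality as Appendix 12.2 defines it. The appendix also provides for central-laboratory alerts on moderate and severe abnormality, and for possible SAE reporting of severe ones. Section 7.5 names liver tests as a point of special emphasis in the safety analysis.

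A reader of the study report will take a by-arm percentage headed Severe Liver Abnormality to be the category that sites and the central laboratory worked with. It is not, and it will not reconcile with the alerts and sponsor contacts. The SAP gives no reason for the narrower definition. The SAP is based on protocol version 2.2 and the current protocol is version 3.0, but the stated purposes of that amendment include no change to liver criteria, so the version gap does not explain the difference.

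**Working it through.** No sample size, power or event figure is at issue, so the check is to apply both classification rules to the same hypothetical subjects. AT is the higher of ALT and AST, and TBL is total bilirubin, both in multiples of ULN.

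**Protocol rule (Appendix 12.2).** Severe if any of these holds: (1) AT > 3 and TBL > 2; (2) AT > 8; (3) AT > 5 on samples more than 14 days apart; (4) AT > 3 and INR > 1.5; (5) AT > 3 with a listed symptom or sign. Otherwise moderate if AT > 3 or TBL > 2. Route 1 is read as concurrent, because the asterisk on the appendix's severe entry leads to the Hy's Law note under Study Discontinuation, which describes raised bilirubin with a concurrent transaminase elevation.

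**SAP rule (Table 8).** Severe row: AT > 3 and TBL > 2 on one sample. Moderate row: AT > 3 or TBL > 2. Separate row: AT > 8.

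| Subject | Protocol | SAP rows met |
|---|---|---|
| A: AT 4, TBL 2.5, same sample | severe (route 1) | Severe, Moderate |
| B: AT 9, TBL 1 | severe (route 2) | Moderate; above-8 row |
| C: AT 6 on days 28 and 56, TBL 1 | severe (route 3; 56 − 28 = 28 days, over 14) | Moderate; above-5 liver-test count, which has no duration rule |
| D: AT 4, INR 1.8, TBL 1 | severe (route 4) | Moderate |
| E: AT 4 with symptoms, TBL 1 | severe (route 5) | Moderate |
| F: AT 4 on day 28, TBL 2.5 on day 56 with AT 1 | moderate | Moderate |
| G: AT 4 only | moderate | Moderate |

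The SAP's Severe row therefore carries 1 of the 5 routes. Subjects B to E are severe in the protocol and absent from that row.

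**What can be derived.** Routes 2 and 3 need only dated ALT and AST results. These are in the central-laboratory panel (Protocol Table 6), and the appendix requires repeat testing after an elevation. INR is not in Table 6. The symptom route needs adverse-event data or the liver abnormality form, although eosinophils are in the central-laboratory differential.

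**What is shown elsewhere.** SAP Section 7.5.2.1 provides that individual displays "will be reported for all subjects with either ALT or AST > 3 x ULN or total bilirubin > 2 x ULN". Every protocol route requires AT above 3 (routes 2 and 3 imply it, since 8 > 3 and 5 > 3). So every protocol-severe subject in the Safety Emergent Period has an individual display.

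**The case against.** The strongest reply is that nothing is lost. Subjects above 8 times ULN have their own row, all protocol-severe subjects are displayed individually, and Table 8 is a table of laboratory criteria, where INR and symptoms do not naturally belong. Appendix 12.2 governs monitoring at sites, and Protocol Section 7.5.2 does not promise a tabulation built on it. All of this stands, and it confines the point to a label, a count and one missing row. It does not answer that point: individual displays give no between-arm rate, and the above-5 threshold carries no duration rule. The liver summary in SAP Section 7.5.2.1 follows a sponsor standard table that is not in the documents, so the most that can be said is that no row for the sustained criterion is visible.

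Three stronger readings are tempting but not supported.

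- **That the same-sample footnote narrows the protocol and misses delayed bilirubin rises.** The protocol's severe entry points to a note that speaks of concurrent elevation, and one blood sample is a reasonable working form of that. Subject F is not clearly severe in the protocol. Nor would F be hidden: Section 7.5.2.1 plots on-treatment maxima of the enzymes and bilirubin against each other with no same-sample condition, and displays such subjects individually.
- **That severe cases are reclassified as moderate.** The rows overlap. Moderate is an either/or rule that every SAP-severe subject also meets. Subjects B to E are missing from the Severe row; they are not moved into an exclusive lower class.
- **That the severe count is biased low overall.** Omitting routes can only lower it, but the protocol grades confirmed abnormalities and Table 8 states no confirmation requirement, which can raise it. The net direction against the full protocol category is not determined.

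**Conclusion.** The point holds as a mismatch of definition. Table 8's Severe row covers one of five protocol criteria. Two of the four it omits can be derived from laboratory data already collected, and one of those two, ALT or AST above 5 times ULN for more than 2 weeks, has no visible row anywhere in the SAP. The other two can be used only where INR or symptoms were recorded.

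The consequence is a by-arm percentage that does not mean what its label says. It is not a loss of safety data. The documents give no liver event rates, so the number of subjects affected cannot be estimated; it is assumed to be small. The conclusion also assumes that the protocol's joint transaminase and bilirubin criterion is read as concurrent, and that the unseen sponsor standard table adds no duration rule.

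**What to change.** Reconcile Table 8 with Protocol Appendix 12.2 in one of two ways:

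1. Extend the Severe row to include ALT or AST above 8 times ULN, and ALT or AST above 5 times ULN on samples spanning more than 2 weeks, with the INR and symptom criteria added where they were recorded.
2. Rename the row ALT/AST >3x and TBL >2x ULN, and state in a footnote that it is not the whole of the protocol's severe category.

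In either case add a by-arm row for ALT or AST above 5 times ULN for more than 2 weeks, and state how an intervening value at or below 5 times ULN is handled. The Moderate row can stay as it is, because every severe route still meets it. Keep the same-sample rule as the working form of concurrent. Do not add a row pairing bilirubin with a transaminase elevation at any other time: neither document defines one, and over up to 104 weeks of treatment it could join unrelated events.

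The cost is SAP wording and modest programming on laboratory and liver-form data already collected. No visit, test or clinical rule changes. Under the first option the reported severe count may be slightly higher.
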